Site personnel will enrol patients using an internet-based system hosted by the ANZIC Research Centre. Randomisation to either the PHARLAP group or the control group will be by permuted blocks and stratified for centre and for the cause of ARDS (direct or indirect)⁴⁸.

Co-enrolment

Co-enrolment of patients into other interventional studies will be decided by the PHARLAP and the co-enrolling study management committees on a case-by-case basis. Participants can be co-enrolled in observational studies.

PARTICIPATING STUDY SITES

To be confirmed

- Albury Wodonga Health
- CVICU, Auckland City Hospital
- DCCM, Auckland City Hospital
- Austin Hospital
- Barwon Health (Geelong Hospital)
- Flinders Medical Centre
- John Hunter Hospital
- King Abdulaziz Medical City for National Guard (Riyadh)
- Lyell McEwin Hospital
- Middlemore Hospital
- Nepean Hospital
- Northern Hospital
- Launceston
- Prince Charles Hospital
- Royal North Shore
- Royal Prince Alfred
- St Vincents Hospital (Dublin)
- The Alfred Hospital
- Wellington Hospital
- Wollongong Hospital

STUDY PROCEDURES

Commencement of mechanical ventilation strategy

Patients in both groups should be commenced on the assigned mechanical ventilation strategy as soon as possible (but no later than 4 hours) after randomisation.

Prior to changing the pre-randomisation mechanical ventilation settings to the assigned strategy, 3 tasks need to occur in the following order in both groups of patients:

1. Predicted body weight should be estimated.
2. Static respiratory compliance should be measured (see below).
3. Specimens of blood and BAL should be collected (see below) – after static respiratory compliance has been measured.

Estimation of predicted body weight:

Before setting up the ventilator strategy, the patient's predicted body weight must be determined. This should be estimated using a formula which requires height⁴⁹ (Appendix 1). If there has been no recent (last few days) measurement of height, the height should be estimated using a formula which requires measurement of the demi-arm span (Appendix 1).

Measurement of static respiratory compliance:

- The patient should be adequately sedated (no spontaneous breaths).
- An expiratory pause of 5 seconds should be set to measure intrinsic PEEP (PEEPi). If the 5 second pause can not be achieved (because the next breath occurs before the end of the pause), a shorter pause should be set.
- Total PEEP is calculated as PEEPi + set PEEP.

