- The expiratory pause should be removed, and 30 seconds waited, before a 0.5 second inspiratory pause should be set to measure plateau pressure.
- Within the same breath, expired tidal volume and plateau pressure should be measured.
- Static respiratory compliance should be calculated as tidal volume / (plateau pressure – total PEEP).

Collection of specimens at baseline:

Patients in both groups should have specimens of blood and bronchoalveolar lavage (BAL) fluid collected prior to commencement of the assigned mechanical ventilation strategy.

The blood specimen should be collected from the arterial line and sent with the BAL specimen to the site's pathology department for appropriate spinning and storage. These will be sent in batches to Flinders Medical Centre for measurement of IL-6 and IL-8 levels in both blood and BAL.

To perform the BAL, we recommend using a bronchoscopic method. Alternatively a non-bronchoscopic technique using the KimVent BAL Cath (Bronchial Aspirate Sampling Catheter) can also be used. There are two sizes of KimVent BAL Caths – 13F is recommended for a size 7cm ETT and smaller and 16F is recommended for a size 7.5cm ETT and larger. These will be provided to all sites by the ANZIC-RC. Whichever method is used, at least 10 ml of BAL fluid should be collected. A right-sided BAL is preferred for consistent sampling.

Appendix 2 includes instructions on how to collect the specimen if a bronchoscopic method is used. It also includes instructions on how to perform the non-bronchoscopic technique using the KimVent BAL Cath to collect the BAL specimen.

If the patient has been assigned to the PHARLAP group, this procedure should now be followed as soon as possible (but no later than 4 hours after randomisation) by a combined open lung procedure (see below). Satisfactory haemodynamic resuscitation may also be required before 4 hours after randomisation.

If it is not feasible to collect a BAL sample because of limited resources to perform the bronchoscopy or the Investigator is unfamiliar with the use of the KimVent BAL cath or it may cause undue delay in recruitment then

a BAL sample is not required to be collected once enrolled. We understand that this may occur from time to time. However, every attempt should be made to collect the blood sample on all patients.

Control group mechanical ventilation

Initial commencement of mechanical ventilation in the control group

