APPENDIX 3: SCHEDULE OF EVENTS

Assessments/ Procedures	Pre Randomisation/ Baseline	Day 1	Day 2	Day 3	Day 4	Day 5	Day 6 till liberation of mechanical ventilation	ICU discharge	Hospital discharge	Follow-up 28 days	Follow-up 90 days	Follow-up 6 months
Inclusion & Exclusion criteria	X											
Consent	X											
Randomisation	X											
Demographic data	X											
Height & weight measurement	X											
CXR	X											
Download CXR image	X											
Apache II score	X											
Apache III diagnosis	X											
SOFA score	X	X	X	X	X	X	X					
Ventilation observations	X	X	X	X	X	X	X					
Static respiratory compliance		X		X								
Combined open lung procedure		X*	X*	X*	X*	X*						

* Only for patients randomised to PHARLAP treatment group (combined open lung procedure)

Assessments/ Procedures	Pre Randomisation/ Baseline	Day 1	Day 2	Day 3	Day 4	Day 5	Day 6 till liberation of mechanical ventilation	ICU discharge	Hospital discharge	Follow-up 28 days	Follow-up 90 days	Follow-up 6 months
Sputum sample (BAL)		X		X								
Blood sample		X		X								
Adverse events		X	X	X	X	X	X	X				
Serious adverse events		X	X	X	X	X	X	X	X			
Survival status								X	X	X	X	
SF36V ₂												X
EQ5D												X

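### Baseline lavage is taken, and may be waived, after the arm is known, so loss from the lavage IL-6/IL-8 outcome can depend on allocation

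*Combined protocol and SAP*

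**What the plan says.** Under Commencement of mechanical ventilation strategy, both arms start the assigned strategy "as soon as possible (but no later than 4 hours) after randomisation". The same section continues: "Prior to changing the pre-randomisation mechanical ventilation settings to the assigned strategy, 3 tasks need to occur". The tasks are predicted body weight, static compliance, and then blood and lavage. Collection of specimens at baseline repeats that specimens are "collected prior to commencement of the assigned mechanical ventilation strategy", which is a limit relative to the ventilator change and not to randomisation. Appendix 3 agrees: compliance, lavage and blood are marked at Day 1 and Day 3, and the pre-randomisation column is empty for them.

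The arm is known at this moment, because the next step depends on it: "If the patient has been assigned to the PHARLAP group, this procedure should now be followed as soon as possible", the next step being the combined open lung procedure.

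The same section then waives lavage. If bronchoscopy resources are limited, if the investigator is unfamiliar with the catheter, or if "it may cause undue delay in recruitment", then "a BAL sample is not required to be collected once enrolled". Blood is still to be attempted in every patient, and no waiver is given for compliance.

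The secondary outcome is the change in lavage IL-6 and IL-8 from baseline to day 3. Appendix 7 uses the same change by radiological subtype. Laboratory sampling states that the laboratory scientists are blinded. The Statistical and analytical plan section says that analyses are by intention to treat, but gives no rule for missing samples.

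**The concern.** A change score needs both samples. Whoever decides whether to lavage at baseline therefore decides whether the patient can enter the lavage comparison, and makes that decision with the arm known. Blinding the laboratory protects the assay but not the choice of whom to sample.

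The pressure to omit is not the same in the two arms. The 4-hour limit is common, but a control patient needs only a change of ventilator settings, whereas a PHARLAP patient must also complete the combined open lung procedure after haemodynamic resuscitation. If omission tracks both arm and severity, the lavage result compares groups selected after allocation. Labelling the analysis intention-to-treat does not restore patients who have no baseline. Nothing in the text requires the reason for omission to be recorded or availability to be reported by arm, so a reader of the results could not judge the problem.

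**Working it through.** **The plan's own figures.** None exists for lavage: no effect size, sample size or expected missingness. The stated 282, 324 and 340 concern ventilator-free days and reproduce approximately. With 3 days and an SD of 9 (3 days being 33% of an SD), two-sided 0.05, 80% power and equal arms, n per arm = 2(1.960 + 0.842)²/(3/9)² ≈ 142, or 284 in total. Then 282 × 1.15 = 324.3 and 324 × 1.05 = 340.2. This point does not touch them.

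**Extra load in PHARLAP.** From the section on the combined open lung procedure: adjusting inspired oxygen often takes 15–30 minutes, the staircase 3 × 2 = 6 minutes, PEEP titration up to 5 × 3 = 15 minutes, and the brief manoeuvre 2 minutes. The upper end is 30 + 6 + 15 + 2 = 53 of 240 minutes, plus any resuscitation. Lavage itself begins by raising inspired oxygen to 1.0 (Appendix 2), which the procedure must then bring back down. The competition is real but need not fill the window.

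**Illustration A (every input is an assumption).** Let u be the share of unstable patients, s the rate at which they are sampled relative to the others, and d the difference in cytokine change between unstable and other patients, in SD.

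Unstable share among those sampled = u·s / (u·s + 1 − u). Bias = difference in that share between arms × d.

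| Assumption | Control share | PHARLAP share | Bias for d = 0.5 to 1.0 |
|---|---|---|---|
| u = 30%; s = 1 control, 0.5 PHARLAP | 30% | 0.15/0.85 = 17.6% | 0.06 to 0.12 SD |
| u = 30%; s = 0.75 control, 0.5 PHARLAP | 0.225/0.925 = 24.3% | 17.6% | 0.03 to 0.07 SD |
| u = 10%; s = 1 control, 0.5 PHARLAP | 10% | 0.05/0.95 = 5.3% | 0.02 to 0.05 SD |

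The sign follows d. If unstable patients show the worse change, the bias favours PHARLAP. If they start higher and fall further, the same amounts count against it.

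**Illustration B (different assumptions, no true effect, 170 per arm).** Control lacks 10% at random. PHARLAP lacks a larger share m, the extra omissions being the sickest patients, with correlation ρ = 0.2 to 0.5 between severity and outcome. With e = (m − 0.10)/0.90, the shift is ρ·φ(z₁₋ₑ)/(1 − e).

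| PHARLAP missing | Shift | Type I error (nominal 5%) |
|---|---|---|
| 20% | 0.04 to 0.11 SD | 6.5% to 15% |
| 30% | 0.08 to 0.19 SD | 10% to 35% |
| 40% | 0.11 to 0.27 SD | 14% to 57% |

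B is deliberately strict, since all extra omissions fall on the sickest. Neither illustration estimates this trial. They show that the answer runs from negligible to material according to rates that the documents do not give.

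**The case against.** Several stronger readings are tempting, and the documents do not support them.

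- *All the baselines can go missing selectively.* The waiver covers lavage only. Blood and compliance are also taken after allocation, but their omission is not permitted.
- *The deadline presses on PHARLAP alone.* The 4-hour limit is set for both groups. Where a recruitment manoeuvre is contraindicated, the protocol defers the open lung procedure, which relieves the clock for some unstable patients.
- *The delay waiver exists in one arm only.* That holds only if the word means lung recruitment. The protocol also uses it for enrolment, in the feasibility section and the timeline, although that sense sits awkwardly with a waiver that applies once the patient is enrolled. The text does not settle it.
- *The bias flatters PHARLAP.* The direction depends on how sicker patients' cytokines change, on which the documents are silent.
- *The bias is a large fraction of the trial's effect.* The 0.33 SD was set for ventilator-free days, so it is no yardstick for lavage cytokines.

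It is also fair that the other two waiver reasons are mainly site matters and randomisation is stratified by centre; that instability is not a listed reason and marked cardiovascular instability is an exclusion; that samples precede the ventilator change; and that plasma cytokines remain as a counterpart. The full analysis plan is still to be finalised and could deal with missing samples.

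These points limit the concern to one secondary biomarker and its substudy use. They do not remove it. The decision to omit is still made with the arm known, and a later analysis plan cannot make a selection independent of arm after the fact.

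**Conclusion.** The point holds for baseline lavage. As written, the plan allows arm-dependent loss from the lavage IL-6/IL-8 change outcome and from the lavage part of the Appendix 7 substudy, where only 40 to 50 patients per arm per subtype are expected. Knowledge of the arm is inferred from the arm-specific bedside procedures.

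Size and direction are unknown. The 0.06 to 0.12 SD figure rests on 30% unstable patients, a 0.5 to 1.0 SD difference in their cytokine change, and half-rate sampling of them in PHARLAP against full sampling in control. Milder inputs give 0.02 to 0.07 SD, and stricter selection gives more. The primary outcome and its sample size are unaffected. This is an inexpensive improvement to a secondary outcome, not a flaw in the main comparison.

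**What to change.** 1. Add a field to the web randomisation form, completed before the arm is shown: *baseline lavage will be done: yes/no; method; reason if no*. All three waiver reasons can be known by then.
2. Remove delay to recruitment as a reason to waive after allocation, or define the term so that it applies equally to both arms before allocation.
3. Define the lavage comparison population as patients recorded as yes. The field alone does not prevent a yes patient from going unsampled, so report by arm, with reasons, every such patient lacking a baseline or day-3 sample.
4. Pre-specify a sensitivity analysis for those missing samples. Earlier baseline sampling cannot prevent day-3 losses, so this is needed in any case.
5. Where feasible, take baseline compliance, blood and lavage after consent and before randomisation, and move them to the pre-randomisation column of Appendix 3. Compliance gains too, because its baseline feeds the day-3 lack-of-improvement rule and the responder subgroup. The protocol asks that lavage in PHARLAP be followed promptly by the open lung procedure, and this change puts the randomisation step between them, so the investigators must judge whether it is workable.

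Cost: one form field, some added time before randomisation, a few patients sampled but not randomised, and a somewhat smaller lavage analysis set. In return, sampling done before randomisation no longer uses up the 4-hour window, which runs from randomisation.

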- Within 72 hours of mechanical ventilation for a diagnosis of ARDS (moderate and severe) based on the Berlin definition⁴⁷
 - Within 1 week of a known clinical insult or new or worsening respiratory symptoms
 - Bilateral opacities on CXR which are not fully explained by effusions, lobar/lung collapse or nodules
 - Respiratory failure not fully explained by cardiac failure or fluid overload
 - $\text{PaO}_2/\text{FiO}_2 < 200$ mmHg with $\text{PEEP} \geq 5$ cmH₂O

Exclusion criteria

- > 72 hours since diagnosis of ARDS
- > 10 days of continuous mechanical ventilation
- < 16 years of age
- Barotrauma (pneumothorax, pneumomediastinum, subcutaneous emphysema or any intercostal catheter for the treatment of air leak)
- Significant chest trauma i.e. multiple rib fractures
- Active bronchospasm or a history of significant chronic obstructive pulmonary disease or asthma
- Clinical suspicion for significant restrictive lung disease (history of pulmonary fibrosis or suggestive pulmonary function tests)
- Moderate or severe traumatic brain injury, the presence of an intracranial pressure monitor, or any medical condition associated with a clinical suspicion of raised intracranial pressure
- Unstable cardiovascular status defined as sustained heart rate < 40 or > 140 bpm, ventricular tachycardia, or SBP < 80 mmHg
- Pregnancy
- Receiving ECMO
- Receiving high frequency oscillatory ventilation
- Death is deemed imminent and inevitable
- The treating physician believes it is not in the best interest of the patient to be enrolled in the trial
- Consent not obtained or refused by patient's legal surrogate

Patient screening

Patients will be screened for eligibility criteria in 25-30 ICUs in Australia and New Zealand.

Informed consent

Patients will be unable to provide prospective informed consent, as they will be sedated and receiving mechanical ventilation. Informed consent will be obtained from the most appropriate Person Responsible, in accordance with section 4.4.10 of the NHMRC National Statement, and with variations according to state and territory legislations (and also as appropriate for New Zealand). Delayed consent for long-term follow up will be sought from the participant when they have suitably recovered capacity.

Enrolment and randomisation

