Please see the section below on “Weaning of mechanical ventilation for both groups”

Intervention group (PHARLAP) mechanical ventilation

Initial commencement of mechanical ventilation in the PHARLAP group

Mode: After randomisation, patients should be commenced in either Assist-Control (A/C) or Synchronised Intermittent Mandatory Ventilation (SIMV) using Pressure Control mode. All patients should be commenced in controlled rate ventilation, even if this requires additional sedation and/or neuromuscular blocking drugs. The PEEP level should remain at the pre-randomisation level.

The combined open lung procedure in the PHARLAP group (see Figure 1)

The initial procedure of the PHARLAP mechanical ventilation strategy should be to perform the combined open lung procedure which consists of (1) a staircase recruitment manoeuvre (SRM), followed by (2) a PEEP titration manoeuvre, and followed by (3) a brief recruitment manoeuvre (see Figure 1). This initial combined open lung procedure should be performed within 4 hours of randomisation.

This will then be followed by PHARLAP strategy mechanical ventilation.

The combined open lung procedure should be performed after assessment by an intensivist or registrar and when haemodynamic resuscitation is complete and circulatory parameters are stable. If vasopressors or inotropes are being used, a small transient increase prior to the combined open lung procedure will minimise any hypotension.

The **contraindications to a recruitment manoeuvre** (both the staircase and the brief manoeuvre) are:

- Mean systemic blood pressure < 60 mmHg despite attempts to augment BP with vasopressors/fluids.
- An active air leak through an intercostal catheter.
- Any radiographical evidence of pneumatoceles, subpleural cysts, or pericardial or mediastinal emphysema.
- Subcutaneous emphysema not related to trauma, surgical procedures, or ICU procedures.
- A supraventricular tachycardia associated with a mean systemic blood pressure < 70 mmHg, or any ventricular tachycardia.

If a patient has a contraindication to the combined open lung procedure, all other aspects of PHARLAP mechanical ventilation should be continued until the contraindication has resolved (when the combined open lung procedure should then be performed).

The combined open lung procedure should be performed as follows:

(1) Staircase recruitment manoeuvre (SRM):

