The mechanical ventilator settings should be Pressure Control with an inspiratory pressure of 15 ± 3 cmH₂O depending on tidal volume achieved (pre-SRM tidal volume target 4-6 ml/kg PBW). The PEEP level should be left at the level it had been immediately prior to this procedure. The FiO₂ should be adjusted (usually by turning it down) until the SaO₂ is stable between 90-92%. This may take several (often 15-30 minutes). The high pressure alarm should be set to 65 cmH₂O and the low tidal volume and minute ventilation alarms reduced to < 25% of the current settings.

Once the FiO₂ is stable (ie. no change for 3 minutes), the PEEP should be increased from the pre-randomisation baseline to 20 cmH₂O. In a stepwise fashion, this should be increased after 2 minutes to 30 cmH₂O (for 2 minutes) and then 40 cmH₂O (for 2 minutes), unless there is occurrence of (a) haemodynamic instability (defined as heart rate < 40 or > 140 bpm, ventricular tachycardia, or systolic blood pressure (SBP) < 80 mmHg), (b) marked oxygen desaturation (SaO₂ < 85%) or (c) new air leak through an intercostal catheter. The tidal volume should not be adjusted at each PEEP level, unless the tidal volume is > 6 ml/kg PBW.

The patient may cough or become restless at high PEEP levels. This may be due to expansion of collapsed lung and does not require the SRM to be discontinued. Transient reductions in tidal volume and minute ventilation are to be expected as the PEEP levels are increased. Sometimes the patient will require additional sedation.

If haemodynamic instability, marked oxygen desaturation or a new air leak occurs during the SRM, the SRM should be abandoned (with no further increases in PEEP occurring above the level where this occurred). If the

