patient is considered to be inadequately haemodynamically resuscitated for their underlying condition, then it is preferable if vasopressor or fluid resuscitation should occur over the next 30-60 minutes, and then the combined open lung procedure be resumed. If the patient is considered to be adequately haemodynamically resuscitated, then fluid loading purely for the SRM should not be undertaken. The PEEP level one level below the PEEP level at which the SRM was abandoned should be determined as the **maximum tolerated PEEP** for this specific SRM and the PEEP titration manoeuvre should now occur (i.e. if marked desaturation occurs at 40 cmH₂O the maximum tolerated PEEP should then be determined as 30 cmH₂O). The maximum tolerated PEEP for the SRM will be determined daily and may be a different value on subsequent days.

If there is no occurrence of haemodynamic instability, marked oxygen desaturation or new air leak, the PEEP should be increased to the highest level of 40 cmH₂O. This should be determined as the maximum tolerated PEEP for this SRM.

(2) PEEP titration manoeuvre

After the final SRM step has been completed (or abandoned, as above), the PEEP should be immediately reduced to 25 cmH₂O. If, however, the SRM was abandoned at 20 cm H₂O, the PEEP titration should begin at 17.5 cm H₂O. The PEEP should be left at this first setting for 3 minutes, then decreased in steps by 2.5 cmH₂O for 3 minutes at each PEEP level to a minimum of 15 cmH₂O (i.e. from 25 to 22.5 to 20 to 17.5 to 15 cmH₂O) until the **de-recruitment PEEP** is reached. If the mechanical ventilator does not have 0.5 cmH₂O increments, round the PEEP up from 22.5 to 23 and 17.5 to 18 cmH₂O. The de-recruitment PEEP is defined as the PEEP level at which the SaO₂ first decreases by $\geq 2\%$. Once the de-recruitment PEEP has been reached, there should be no further reduction in PEEP, and the brief recruitment manoeuvre should now occur.

The PEEP should not be reduced below 15 cmH₂O if desaturation does not occur. In this situation, the PEEP should be left on 15 cmH₂O and no brief recruitment manoeuvre is required (i.e. the combined open lung procedure has been completed).

(3) Brief recruitment manoeuvre

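### The steps after a new air leak lead to a brief recruitment manoeuvre that the contraindication list bars, and pneumothorax is missing from that list and from the staircase stop rules

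*Combined protocol and SAP*

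**What the plan says.** The section on the combined open lung procedure gives one list of contraindications and says that it covers "both the staircase and the brief manoeuvre". Two of its entries concern air outside the lung directly: "An active air leak through an intercostal catheter" and "Any radiographical evidence of pneumatoceles, subpleural cysts, or pericardial or mediastinal emphysema". A third is subcutaneous emphysema, unless explained by trauma, surgery or an ICU procedure. While a contraindication is present, "all other aspects of PHARLAP mechanical ventilation should be continued until the contraindication has resolved".

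The numbered steps follow in the same section:

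- **Staircase.** A new air leak through an intercostal catheter is one of three grounds for stopping: "If haemodynamic instability, marked oxygen desaturation or a new air leak occurs during the SRM, the SRM should be abandoned". The maximum tolerated PEEP then becomes the level one below the stop, and "the PEEP titration manoeuvre should now occur".
- **PEEP titration.** Once SaO2 has dropped by at least 2%, PEEP is lowered no further "and the brief recruitment manoeuvre should now occur".
- **Brief manoeuvre.** It lasts 2 minutes at the maximum tolerated PEEP, with inspiratory pressure 15 ± 3 cmH2O.

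The Exclusion criteria rule out, at entry, "Barotrauma (pneumothorax, pneumomediastinum, subcutaneous emphysema or any intercostal catheter for the treatment of air leak". Under Ongoing recruitment manoeuvres in the PHARLAP group, item (c) of both omission lists (daily combined procedure and independent brief manoeuvre) points back to the contraindication list. The Desaturation paragraph there recommends a chest film to rule out barotrauma before further manoeuvres when desaturation is significant and persists.

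**The concern.** There are two gaps in the wording.

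1. **The leak rule is not carried through.** The steps handle a new air leak like hypotension or desaturation: drop one PEEP level, titrate, then re-recruit. Nothing in the titration or brief-manoeuvre steps says that a leak ends the sequence. Someone working from the steps alone could re-pressurise a lung that has just begun to leak, which the list a few paragraphs above forbids. The plan evidently does not intend this, since elsewhere it counts a new leak as a reason to allow PEEP to be weaned.

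2. **Pneumothorax is not listed.** It bars entry to the trial but, once a patient is enrolled, it is neither a contraindication nor a reason to stop a staircase. The air-leak entries do not fill the gap, because both depend on an intercostal catheter. An undrained pneumothorax therefore falls outside both lists.

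What is at stake is patient safety in one arm. Barotrauma is a named safety outcome, and the Significance section acknowledges concern that staircase manoeuvres and high PEEP may cause it.

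**Working it through.** No statistical figure is involved, so the check sets sections side by side and adds simple pressure arithmetic.

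**Part 1: pressures if the steps are followed literally after a new leak**

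Inputs from the staircase, titration and brief-manoeuvre steps:

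- Staircase PEEP levels are 20, 30 and 40 cmH2O, 2 minutes each.
- Inspiratory pressure is 15 ± 3, that is 12 to 18.
- Titration starts at 25 and falls by 2.5 every 3 minutes to a minimum of 15. It starts at 17.5 if the staircase was abandoned at 20.

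Formulas: total pressure = maximum tolerated PEEP + inspiratory pressure; PEEP change = maximum tolerated PEEP − de-recruitment PEEP.

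| Leak at step | Maximum tolerated PEEP | Total in brief manoeuvre | PEEP change |
|---|---|---|---|
| 40 | 30 | 30+12 to 30+18 = 42 to 48 | 30−25 to 30−15 = +5 to +15 |
| 30 | 20 | 20+12 to 20+18 = 32 to 38 | 20−25 to 20−15 = −5 to +5 |
| 20 | pre-procedure PEEP, assumed 5 to 17.5 | 5+12 to 17.5+18 = 17 to 35.5 | 5−17.5 to 17.5−15 = −12.5 to +2.5 |

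At the 40 step the leak appeared at a total of 40+12 to 40+18 = 52 to 58, so the brief manoeuvre runs 10 cmH2O below that. It still raises PEEP by 5 to 15 for 2 minutes, no more than 5 levels × 3 min = 15 minutes after titration begins.

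The range in the 20 row is an assumption. From day 2 the minimum PEEP of 15 (until weaning readiness) narrows it. A pre-procedure PEEP of 20 or more, which the later-day rules permit, has no lower level defined beneath the 20 step and is not worked here.

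The plan's 25 cmH2O limit on set PEEP names only the staircase as an exception. It follows an instruction that itself takes PEEP to the maximum tolerated level, so it is read here as a limit on the maintained setting, not on the brief manoeuvre.

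**Part 2: entry exclusion against the in-trial lists**

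| Barotrauma item at entry | Contraindication list | Staircase stop rules |
|---|---|---|
| Pneumothorax | none | none |
| Pneumomediastinum | mediastinal emphysema | none |
| Subcutaneous emphysema | listed, with exceptions | none |
| Catheter for air leak | active leak through a catheter | new leak through a catheter |

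Three of the four items have at least a partial counterpart among the contraindications; pneumothorax has none. Because item (c) of both omission lists refers back to the contraindications, the gap passes to every later manoeuvre.

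The independent brief manoeuvre is where this matters most. An SaO2 at least 2% below the daily target with no clear cause leads to 2 minutes at the last maximum tolerated PEEP, which can be 40. PEEP then returns to 2.5 cmH2O above its previous setting. The assessment by an intensivist or registrar is stated for the combined procedure and is not repeated for this manoeuvre.

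**The case against.** **The leak rule already exists.** The contraindication list covers the brief manoeuvre, stands directly above the steps, and need not be repeated at each one. This is right. A reader might infer that the protocol permits recruitment through an active leak; the documents do not support that, because the list is general and should override. What remains is that the step text names a new leak and still directs staff onward, whereas the independent brief manoeuvre has an explicit cross-reference. It can also be said that PEEP 30 had just been held for 2 minutes before a leak at 40. That is true, but it was held before the leak appeared.

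**Listing pneumothorax cannot help if nobody knows it is there.** Also right. A reader might infer that the added entry would prevent harm from a pneumothorax that shows only as unexplained desaturation. It would not; only a required check could. The entry helps where the condition is known or suspected.

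**Other safeguards exist.** Asking for a film to rule out barotrauma beforehand already implies not proceeding if it is positive. There are also senior assessment before the combined procedure, staircase stop limits (SaO2 below 85%, systolic pressure below 80 mmHg, heart-rate limits), and freedom to deviate for an immediate hazard. It would therefore be wrong to say that the plan ignores pneumothorax. But the film is advisory and limited to significant, persistent desaturation, and no action on a positive result is written down.

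**The scenario in part 1 is rare.** Agreed. It needs a catheter present for another reason or placed after entry, a new leak within a staircase of about 3 × 2 = 6 minutes, a saturation fall on titration, and a leak still active then.

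**Conclusion.** Both points hold as a minor safety correction. In the first, two parts of the procedure conflict and the contraindication list should prevail. Among the branches worked, only a leak at the 40 step carries a material PEEP rise (to 30, total 42 to 48 cmH2O). In the second, pneumothorax is absent from the contraindications and the staircase stop rules although it is disqualifying at entry; this carries more of the weight.

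A reader might take a protocol conflict of this kind as a threat to the trial's result. Nothing here bears on the primary outcome, power or bias. The number of patients affected cannot be derived from the documents. The conclusion rests on the text alone: the procedure figure and the bedside ventilation sheet are not shown and may already say what is missing.

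**What to change.** 1. In the PEEP titration and brief-manoeuvre steps, state that after a new air leak the brief manoeuvre is omitted and the rule for contraindications applies, with other PHARLAP ventilation continuing until the leak resolves.
2. Add known or suspected undrained pneumothorax to the contraindication list, so that both item (c) cross-references carry it, and to the staircase stop rules.
3. In the Desaturation paragraph, state that if the film shows a pneumothorax, no staircase or brief manoeuvre is done until it has been drained and there is no active leak.

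The PEEP level to use after a leak, including any exception to the minimum of 15 cmH2O, is for the clinical leads to decide.

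The cost is a few sentences, matching edits to the figure and bedside sheet if they lack these points, and fewer manoeuvres for a few PHARLAP patients. No analysis changes.
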